7.3. Definition of Serious Adverse Events

An SAE is defined as any AE that fulfills one or more of the following criteria:

- Results in death
- Is immediately life-threatening
- Requires inpatient hospitalization or prolongation of existing hospitalization
- Results in persistent or significant disability/incapacity
- Results in congenital anomaly/birth defect
- Is an important medical event that may jeopardize the participant or may require medical intervention to prevent one of the outcomes listed above.

Important medical events that may not meet one of the above criteria could be considered a SAE by the Investigator when, based upon appropriate medical judgment, they are considered clinically significant and may jeopardize the participant, or may require medical or surgical intervention to prevent one of the outcomes listed above.

An AE is considered "life-threatening" if, in the opinion of either the Investigator or the Sponsor, its occurrence places the participant at immediate risk of death. It does not include an AE that, had it occurred in a more severe form, might have caused death.

7.3.1. Protocol Specific Disease Progression Adverse Event and Serious Adverse Event Reporting Requirements

Disease progression in this study is measured via the CDR-SB. Changes in these scores that are consistent with the expected rate of progression of the underlying disease should not be recorded as AEs.

However, symptomatic deterioration or events that are judged by the Investigator to be inconsistent with normal disease progression or are considered related to study drug should be reported as AEs, and if any of the "serious" criteria are met, it must be reported as an SAE.

Please note that the term "disease progression" should not be reported, but rather the clinical manifestation(s) with applicable descriptors should be captured on the AE eCRF page.

7.4. Definition of Clinical Laboratory Abnormalities and Other Abnormal Assessments as Adverse Events/Serious Adverse Events

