To maintain consistency of reporting across clinical sites, findings of ARIA-E or ARIA-H on MRI are determined by the MRI Central Reader by radiologists with expertise in assessing for ARIA and other abnormalities on brain MRI. ARIA-E, ARIA-H and other findings are documented on and reported to the sites with the BMW report (see Section 6.5.12). The BMW provided by the Central Reader after each MRI examination scores ARIA-E (parenchymal vasogenic edema, leptomeningeal/sulcal effusion) according to: extent, location, number of sites involved, radiographic severity (mild, mild+, moderate, moderate+, severe) (Table 6) and changes since prior MRI exams. ARIA-E findings typically resolve radiographically and will be noted as such on the BMW of follow-up MRI scans. The BMW also documents occurrence and characteristics (location, size, number) of ARIA-H (parenchymal microhemorrhages and leptomeningeal hemosiderosis and macrohemorrhages).

Overall, ARIA-H radiographic severity is defined as the worst individual radiographic severity for microhemorrhages, leptomeningeal hemosiderosis or macrohemorrhages (eg, if there are

Alector, Inc.

4 incident microhemorrhages, 1 incident areas of leptomeningeal hemosiderosis and no macrohemorrhages, then ARIA-H is rated as "Moderate") (Table 6).

Table 6: ARIA-E and ARIA-H Radiographic Severity Scales

ARIA-E Characterization:		Severity/Grade	
<5 cm monofocal		Mild (Grade 1)	
<5 cm multifocal		Mild+ (Grade 2)	
5-10 cm monofocal	N	Moderate (Grade 3)
5-10 cm multifocal	Moderate+ (Grade 4)		
>10 cm monofocal/multifocal	Severe (Grade 5)		
Incident ARIA-H:	Mild	Moderate	Severe
microhemorrhages	1-4	5-9	10 or more
Areas of leptomeningeal hemosiderosis	NA	1	2 or more
macrohemorrhages	NA	NA	1 or more

ARIA-E=amyloid-related imaging abnormalities-edema; ARIA-H=amyloid-related imaging abnormalities-hemosiderin deposits; NA=not applicable.

ARIA-H findings very rarely resolve radiographically; it is more typical for ARIA-H findings to stabilize radiographically. Radiographic stabilization of an ARIA-H finding is defined as when a follow-up MRI scan shows no increase in number/size/extent of previously seen cerebral microhemorrhages, leptomeningeal hemosiderosis and cerebral macrohemorrhages.

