Participants in Part 1 with MRI evidence of ARIA at the Day 15 or Day 43 MRI will be discontinued from study drug administration. Participants in Part 1 with ARIA after Day 43 and participants in Part 2 with MRI evidence of ARIA at any visit will be managed according to the guidelines in Table 7.

AL002 Alector, Inc.

Table 7: Dosing Guidelines for ARIA

Finding	Asymptomatic/Symptomatic	Action	
Milda ARIA-E	Asymptomatic or Symptomatic	Suspend dosing until resolution of ARIA-E or	
Moderate ^b ARIA-E	Asymptomatic or Symptomatic	stabilization of ARIA-H. After resolution (ARIA-E) and/or stabilization (ARIA-H), if	
Severe ARIA-E	Asymptomatic or Symptomatic	participant dosing is restarted, they must receive the same dose they received immediately prior	
Mild or Moderate ARIA-H	Asymptomatic	to the ARIA-E/ARIA-H findings and continue on that dose for the remainder of the study. After resuming dosing, 5-10 days before their second post-resumption dose, participants must undergo an unscheduled MRI that must be assessed by the Central Reader for ARIA-E/H before the next dose is administered.	
		For mild or moderate symptomatic ARIA-E the use of oral or IV steroids can be considered.	
		For severe symptomatic ARIA-E it is recommended to hospitalize the participant for close observation and consider the use of IV steroids such as high-dose dexamethasone or a similar agent.	
Mild or Moderate ARIA-H	Symptomatic	Permanently discontinue treatment	
Severe ARIA-H	Asymptomatic or Symptomatic	Permanently discontinue treatment	
Serious ^c ARIA-E or Serious ARIA-H	Symptomatic	Permanently discontinue treatment	
Serious ^c ARIA-E or Serious ARIA-H	Asymptomatic	Suspend dosing until resolution of ARIA-E or stabilization of ARIA-H. After resolution (ARIA-E) and/or stabilization (ARIA-H), if participant dosing is restarted, they must receive the same dose they received immediately prior to the ARIA-E/ARIA-H findings and continue on that dose for the remainder of the study. After resuming dosing, 5-10 days before their second post-resumption dose, participants must undergo an unscheduled MRI that must be assessed by the Central Reader for ARIA-E/H before the next dose is administered.	
A second occurrence of ARIA-E after full resolution of a prior occurrence of ARIA-E	Asymptomatic or Symptomatic	Permanently discontinue treatment	

ARIA-E=amyloid-related imaging abnormality-edema; ARIA-H=amyloid-related imaging abnormality-hemosiderin deposits; MRI=magnetic resonance imaging.

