^a Mild includes 'mild' and 'mild+', as scored on the BMW from the Central Reader.

^b Moderate includes 'moderate-' and 'moderate+', as scored on the BMW from the Central Reader.

^c Meets criteria for a SAE.

AL002 Alector, Inc.

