#### 6.3.7.2.2 Severity Definition

Individual radiographic severity for microhemorrhages, leptomeningeal hemosiderosis and macrohemorrhages is defined in Table 6-4. ARIA-H radiographic severity is defined as the worst individual radiographic severity among microhemorrhages, leptomeningeal hemosiderosis and macrohemorrhages for an MRI scan as captured in its BMW. If any macrohemorrhages are present at an MRI scan, then the ARIA-H radiographic severity is severe. If macrohemorrhages are absent at an MRI scan, then the worse severity between microhemorrhages and leptomeningeal hemosiderosis will be the ARIA-H radiographic severity. For example, if there are 4 incident microhemorrhages, 1 incident areas of leptomeningeal hemosiderosis and no presence of macrohemorrhages on a BMW, ARIA-H is rated as "Moderate".

Table 6-4. Definition for Individual Radiographic Severity related to ARIA-H

Incident (CFB) Findings	Mild	Moderate	Severe
Number of microhemorrhages	1-4	5-9	10 or more
Areas of leptomeningeal hemosiderosis		1	2 or more
Presence of macrohemorrhages	_	_	Yes

Protocol No. AL002-2 Last Revision Date: 12 Aug 2025

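### Table 7 of the protocol gives two different dosing actions for radiographically severe, asymptomatic ARIA-H that is also an SAE, and does not say which row governs

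*Protocol*

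**What the plan says.** Protocol Section 7.11.1.2, Table 7, applies to Part 1 participants with ARIA after Day 43 and to Part 2 participants at any visit. Four features matter here.

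- The row labelled "Serious ^c ARIA-E or Serious ARIA-H", asymptomatic, has the action "Suspend dosing until resolution of ARIA-E or stabilization of ARIA-H. After resolution (ARIA-E) and/or stabilization (ARIA-H), if participant dosing is restarted", dosing resumes at the dose given just before the finding. The row sets no limit on radiographic grade.
- The row for severe ARIA-H covers both asymptomatic and symptomatic findings. Its action is "Permanently discontinue treatment".
- Footnote c defines serious: "Meets criteria for a SAE". Section 7.3 lists the SAE criteria, including an event that "Is an important medical event that may jeopardize the participant or may require medical intervention to prevent one of the outcomes listed above". That criterion does not require symptoms.
- Severe is a separate, radiographic scale. Section 7.11 states that "ARIA-H radiographic severity is defined as the worst individual radiographic severity for microhemorrhages, leptomeningeal hemosiderosis or macrohemorrhages", and Table 6 rates one or more macrohemorrhages as severe. SAP Section 6.3.7.2.2 agrees: "If any macrohemorrhages are present at an MRI scan, then the ARIA-H radiographic severity is severe".

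Section 7.5.1 itself separates severity from seriousness. Section 4.3.1 item 5 lists ARIA requiring permanent discontinuation as a possible reason to stop study drug, but refers back to Section 7.11 for what that covers.

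**The concern.** Seriousness and radiographic severity are different axes, so a single ARIA-H event can satisfy the severe row and the serious/asymptomatic row together. One row ends treatment and the other allows another infusion once the finding is stable. A site reading the second row alone could re-dose a participant whom the same table says must stop for good.

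The case is clinically sensible, not contrived. A macrohemorrhage found on a surveillance scan in a participant without symptoms is severe by definition, and an investigator could well judge it an important medical event. Table 7 has a row for serious asymptomatic ARIA, so such events were foreseen. What is at stake is re-exposure after an intracranial hemorrhage, for a drug with ARIA as an identified risk (Section 1.3).

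**Working it through.** The documents give no figure to reproduce. The check treats Table 7 as a decision table and asks which events match both a row permitting a restart and a row requiring a permanent stop.

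**Inputs (Tables 6 and 7, footnotes a to c).** Radiographic grade: mild, moderate, severe. Symptoms: yes or no. SAE: yes or no. For ARIA-E only, first or second occurrence.

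**Number of combinations.** ARIA-E: 3 × 2 × 2 × 2 = 24. ARIA-H: 3 × 2 × 2 = 12. Total: 24 + 12 = 36.

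**Combinations matching both kinds of row.**

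| Event | Row permitting restart | Row requiring stop | Count |
|---|---|---|---|
| ARIA-E, second occurrence | ARIA-E grade row (plus serious/asymptomatic row in 3 of them) | second occurrence (plus serious/symptomatic row in 3 of them) | 3 × 2 × 2 = 12 |
| ARIA-E, first occurrence, serious, symptomatic | ARIA-E grade row | serious/symptomatic | 3 |
| ARIA-H, severe, serious, asymptomatic | serious/asymptomatic only | severe ARIA-H | 1 |
| Total | | | 16 |

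**The 15 ARIA-E overlaps.** Every ARIA-E event has a grade, and every ARIA-E grade row says suspend whether or not there are symptoms. The row "A second occurrence of ARIA-E after full resolution of a prior occurrence of ARIA-E" and, for ARIA-E, the serious/symptomatic row would therefore have no effect unless they override the grade rows. The intent is clear even though it is not written.

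**The one ARIA-H overlap.** No ARIA-H grade row permits a restart for a severe finding. The permission comes only from the serious/asymptomatic row, so the argument from intent above is not available.

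**What the serious/asymptomatic row does overall.** It matches 6 ARIA-E combinations (3 grades × first or second occurrence) and 3 ARIA-H combinations, 9 in all. In 5 (first-occurrence ARIA-E at three grades; mild and moderate ARIA-H) it repeats the action of the grade row. In 4 (three second-occurrence ARIA-E, one severe ARIA-H) another row says stop.

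**Two conventions a reader might apply.**

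- Most restrictive row governs: severe, serious, asymptomatic ARIA-H stops permanently. The serious/asymptomatic row then has no effect anywhere: 5 repeats and 4 overridden.
- Seriousness overrides grade: the same event is suspended and may be restarted.

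For first-occurrence serious symptomatic ARIA-E both conventions give a stop, so those rows do not show which one the table intends.

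**Does follow-up imaging settle it?** Section 7.11 counts ARIA-H as stabilized when a follow-up scan shows no increase. An unchanged macrohemorrhage meets that definition, so the scan does not block a restart. The MRI required after resumption falls 5-10 days before the second resumed dose, that is, after one re-exposure.

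**The case against.** The strongest reply is that the rows do not force incompatible actions. The severe row is an order, while the serious/asymptomatic row only sets conditions on a restart if one happens. A site that never restarts complies with both, and one that restarts breaches one. The severe row also names asymptomatic findings directly, and it would be odd if meeting SAE criteria made management more lenient than for the same non-serious finding. This stands as a good reason to expect most sites to stop. It does not remove the fault: the most-restrictive rule is unwritten, and it leaves one row of the table with no effect.

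Safeguards are also real. Each ARIA event is an AESI, reported to the Sponsor within 24 hours with an automatic alert to the Medical Monitor (Section 7.2). The central reader's worksheet goes to the Sponsor as well as the site (Section 6.5.12). An SAE has its own 24-hour reporting (Section 7.7.1), and the Sponsor or Investigator may stop study drug at any time (Section 4.3.1). These lower the practical risk, but none says which row applies. The 48-hour contact with the Medical Monitor in Section 7.11.1.2 is triggered by symptoms or signs, so it does not cover this case. Table 7 does not require approval for a restart, whereas Table 10 does for re-dosing after a nonserious Grade 3 infusion reaction.

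A reader might infer that second-occurrence ARIA-E is an equal conflict, since three such combinations also match the serious/asymptomatic row. The documents do not support that. The ordinary ARIA-E grade rows create the same overlap, and the second-occurrence row makes sense only as an override.

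**Conclusion.** Table 7 is wrong as written in one place: for radiographically severe, asymptomatic ARIA-H meeting SAE criteria, it both requires a permanent stop and permits a restart, with no precedence stated. The severity is minor. The conclusion rests on the SAE definition not requiring symptoms (Section 7.3) and on severe ARIA-H being a radiographic grade (Table 6; SAP Section 6.3.7.2.2).

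The count of 1 core conflict among 16 overlaps and 36 combinations describes the table's logic. The combinations are unweighted and say nothing about risk. The documents give no frequency for serious asymptomatic ARIA, so the judgement that few participants would be affected is an expectation, not a computed figure.

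A reader might also infer that the protocol directs re-dosing after a macrohemorrhage, or that the trial's efficacy conclusions are at risk. Neither follows. The restart is conditional, and the primary analysis, sample size and error rate do not depend on this wording.

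**What to change.** Add a footnote to Table 7: *If more than one row applies, the most restrictive action applies; permanent discontinuation overrides suspension.* This resolves all 16 overlaps.

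Also limit the serious/asymptomatic row to serious first-occurrence ARIA-E and serious mild or moderate ARIA-H. The row then matches 5 combinations instead of 9 and agrees with the grade rows in all of them. The relabel alone is not enough: it clears only the severe ARIA-H overlap and leaves the other 15, because those also arise from the ARIA-E grade rows.

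The cost is one footnote and one row label, with no change to visits, data collection or analysis.

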7.12. General Safety Monitoring

7.12.1. Special Situations

Special situations are non-standard medical conditions that provide valuable information about an investigational product. All special situations associated with an AE or SAE should be recorded in the EDC system in the AE eCRF. Special situations must be reported within 24 hours of becoming aware.

Special situations are defined as below:

- Overdose: An overdose is any dose of study drug given to a participant or taken by a participant that exceeds the dose described in the protocol. There is no known treatment for AL002 overdose, and all participants should be monitored for AEs.
- Off-label use: Situations where a medicinal product is intentionally used for a medical purpose not in accordance with the authorized product information. It's the use of a pharmaceutical drug for an unapproved indication or in an unapproved age group, dosage or route of administration.
- Misuse: This refers to situations where the IP is intentionally and inappropriately used not in accordance with the prescribed or authorized dose, route of administration, and/or the indication(s) or within legal status of its supply.
- Abuse: This corresponds to the persistent or sporadic, intentional excessive use of IP, which is accompanied by harmful physical or psychological effects.
- Medication error: A medication error is any dose of study drug given to a participant
 or taken by a participant that differs from the dose described in the protocol.
 Medication errors are not likely in the study, as the study drug is administered by IV
 infusion by trained personnel under the supervision of the Investigator or their
 designee.
- Occupational exposure: This corresponds to an IP for human use as a result of one's occupation.
- Lack of efficacy/effect: Efficacy is the ability of a drug, biologic, or device to produce desired therapeutic effect independent of potency (amount of the product needed for desired effect). Lack of efficacy/effect, therefore, is the evidence of less than the expected effect of a product. There might be subpopulations that have a higher risk for lack of efficacy/effect; in order to identify such cases, one needs to consider types of events that may be reported in such situations for the specific product and indications.

7.12.2. Pregnancy

Female participants must be instructed to discontinue all study drugs and inform the Investigator immediately if they become pregnant during the study.

The Investigator must report any pregnancy within 24 hours of becoming aware of it using the paper Pregnancy Report Form. Follow-up information documenting the pregnancy outcome should be reported on the paper Pregnancy Report Form. The site should email the Pregnancy

AL002 Alector, Inc.

Report Form to according to the instructions provided in the Study Specific Regulatory Binder.

The participant must be immediately discontinued from study drug and/or optional Tau PET imaging procedure. An uncomplicated pregnancy will not be considered an AE or SAE, but all pregnancies will be followed until a final outcome is known.

Pregnancies are captured if they occur in female participants or in the sexual partners of male participants from the time the participant is first exposed to the study drug or radiotracer until the SFU visit.

Any congenital abnormalities associated with a pregnancy that occurred during study participation are considered SAEs. The outcome of any pregnancy and complete health information regarding the baby will be recorded in the source documentation and reported to Pharmacovigilance.

Any SAE occurring in association with a pregnancy must be reported to Pharmacovigilance regardless of whether the events are considered related to study drug.

7.12.3. Breastfeeding

Adverse events which occur in infants following exposure to an investigational product from breastmilk should be reported.

AL002 Alector, Inc.

8. STATISTICAL METHODS AND ANALYSIS PLAN

All data for each participant will be listed as collected. The statistical analysis plan (SAP) for interim analysis will be finalized prior to the first interim analysis (if applicable). The SAP for final analysis will be finalized prior to the final database lock. The SAP will provide further details regarding the planned analysis methodology, to address all study objectives. Statistical analysis analyses will be performed using Statistical Analysis System (SAS) software Version 9.4 or higher (SAS Institute Inc., Cary, North Carolina, USA).

Continuous data will be summarized using an 8-point descriptive summary (n, mean, standard deviation, median, interquartile range [25% quartile, 75% quartile], minimum, and maximum) unless otherwise specified in the SAP. Categorical data will be summarized using counts and percentages, unless otherwise specified in the SAP.

For analysis, Day 1 is defined as the day of the first study drug administration. The preceding day is Day -1. Baseline is the last non-missing assessment (scheduled or unscheduled) obtained prior to the first study drug administration, unless otherwise specified in the SAP. Baseline for endpoints that have more than one component is calculated from the individual component baselines, whether or not they were assessed during the same visit, unless otherwise specified in the SAP.

Detailed methodology for summary and statistical analyses of the data collected in this study will be documented in the SAP. Any changes to the data summaries and analyses outlined in this section will be documented in the SAP. Additional statistical analyses other than those described in this section may be performed if deemed appropriate. Any deviations from the analysis planned in the SAP will be justified and recorded in the final clinical study report (CSR).

Study endpoints are provided in Section 2.

8.1. Sample Size Calculations

The primary analysis model is a proportional mixed effect model with repeated measurements (pMMRM) which estimates an average treatment effect over all the post-baseline visits. Our proposed model estimates the weighted average across the time varying components. The model provides a clinically meaningful estimation of the treatment benefit averaged across the full duration of the clinical trial, rather than focusing on a single timepoint at the last visit, which may be a random high/low assessment.

To assess the power of the proposed pMMRM, a simulation experiment was conducted using the planned common close design with CDR-SB assessments at baseline and month 6, 12, 18, and 24. Data on the CDR-SB from clinical trials for AD, that are part of a master dataset, were used as the basis for assumptions for the simulations. A total of 441 patients with a global baseline CDR score of 0.5 and 1.0 were selected from this master dataset and the mean and covariance matrix were estimated using a mixed-effects model for repeated measures (MMRM) model. The mean and covariance were then used in simulations to estimate the power of the study. The following table shows the power based on the planned primary analysis method (pMMRM), for different sample sizes per group and different treatment effect assumptions, under the common close design using a two-sided 10% significance level. Under the common close design, we have assumed that 22% (per visit), 27% (per visit), 44% (total), and 58% (total) of participants will be

AL002 Alector, Inc.

missing CDR-SB data at month 6, 12, 18, and 24, respectively, due to dropout and the common close nature of the study design. A total of 5,000 simulations were run per scenario.

		Assumed Treatment Effe	ct
Sample Size	0%	30% Reduction	40% Reduction
60/group	<10%	59%	78%
70/group	<10%	64%	83%

Power based on a two-sided 10% significance level. A total of 5000 simulations were run per scenario.

Based on the above power calculations, 70 participants per group will provide approximately 83% power to detect at least a 40% reduction in the CDR-SB score between any one dose group and the placebo group. To account for an additional 15 participants who discontinued the study drug prematurely because of the removal of the *APOE* e4-homozygous genotype carriers, 6 participants who were randomized but never received any dose administration, and 27 participants who prematurely discontinued from the study (Section 4.3.3), a total of 82 participants per group is planned to be randomized. The planned total sample size is therefore approximately 328 participants (approximately 82 participants per group).

